### **13.2 Informed Consent**

All patients must be provided a consent form describing this study and providing sufficient information for patients to make an informed decision about their participation in this study. The formal consent of a participant, using the IRB approved consent form, must be obtained before the participant is involved in any study-related procedure. The consent form must be signed and dated by the participant or the participant's legally authorized representative, and by the person obtaining the consent. The participant must be given a copy of the signed and dated consent document. The original signed copy of the consent document must be retained in the medical record or research file.

This study is to be conducted according to the following considerations, which represent good and sound research practice:

CONFIDENTIAL

This document is confidential. Do not disclose or use except as authorized.

- US Code of Federal Regulations (CFR) governing clinical study conduct and ethical principles that have their origin in the Declaration of Helsinki
- Title 21 Part 50 – Protection of Human Subjects  
[www.access.gpo.gov/nara/cfr/waisidx\\_02/21cfr50\\_02.html](http://www.access.gpo.gov/nara/cfr/waisidx_02/21cfr50_02.html)
- Title 21 Part 54 – Financial Disclosure by Clinical Investigators  
[www.access.gpo.gov/nara/cfr/waisidx\\_02/21cfr54\\_02.html](http://www.access.gpo.gov/nara/cfr/waisidx_02/21cfr54_02.html)
- Title 21 Part 56 – Institutional Review Boards  
[www.access.gpo.gov/nara/cfr/waisidx\\_02/21cfr56\\_02.html](http://www.access.gpo.gov/nara/cfr/waisidx_02/21cfr56_02.html)
- Title 21 Part 312 – Investigational New Drug Application  
[www.access.gpo.gov/nara/cfr/waisidx\\_02/21cfr312\\_02.html](http://www.access.gpo.gov/nara/cfr/waisidx_02/21cfr312_02.html)
- State laws
- DF/HCC research policies and procedures  
<http://www.dfhcc.harvard.edu/clinical-research-support/clinical-research-unit-cru/policies-and-procedures/>

It is understood that deviations from the protocol should be avoided, except when necessary to eliminate an immediate hazard to a research participant. In such case, the deviation must be reported to the IRB according to the local reporting policy.

### **13.3 Study Documentation**

The investigator (or a representative) must prepare and maintain adequate and accurate case histories designed to record all observations and other data pertinent to the study for each research participant. This information enables the study to be fully documented and the study data to be subsequently verified.

Original source documents supporting entries in the case report forms include but are not limited to hospital records, clinical charts, laboratory and pharmacy records, recorded data from automated instruments, microfiches, photographic negatives, microfilm or magnetic media, and/or x-rays.

### **13.4 Records Retention**

All study-related documents must be retained for the maximum period required by applicable federal regulations and guidelines or institutional policies.

## **14. STATISTICAL CONSIDERATIONS**

This section outlines the statistical analysis strategy and procedures for the study. If, after the study has begun, changes are made to primary and/or key secondary hypotheses, or the statistical methods related to those hypotheses, then the protocol will be amended (consistent with ICH Guideline E-9). Changes to exploratory or other non-confirmatory analyses made after the protocol has been finalized, along with an explanation as to when and why they occurred, will be listed in the Clinical Study Report (CSR) for the study. Post hoc exploratory analyses will be clearly identified in the CSR. No separate Statistical Analysis Plan (SAP) for the primary, secondary and exploratory endpoints will be issued for this study.

CONFIDENTIAL

This document is confidential. Do not disclose or use except as authorized.

## 14.1 Statistical Analysis Plan

This section contains a brief summary of the statistical analyses for this trial. This trial includes allocation of accrual to two experimental treatment arms (nivolumab monotherapy or nivolumab plus ipilimumab). The outcome of each treatment arm will be assessed relative to appropriate historical controls.

### 14.1.1 Responsibility for Analysis

The statistical analysis of the data obtained from this study will be the responsibility of the biostatistics department of the Dana-Farber/Harvard Comprehensive Cancer Center.

This trial is being conducted as an open-label study, i.e., subjects and investigators will be aware of subject treatment assignments after each subject is enrolled and treatment is assigned.

### 14.1.2 Endpoints

#### 14.1.2.1 Primary Endpoint

The primary endpoint of this study is progression-free survival at six months (PFS-6). PFS-6 is defined as the proportion of participants in the analysis population who remain progression-free for at least six months following initiation of study therapy. Response for the primary analysis will be determined by the investigator assessment.

#### 14.1.2.2 Secondary Endpoints

Secondary endpoints for this study include median PFS, median overall survival (OS), objective radiologic response rate (ORR) and assessment of safety/toxicity.

PFS is defined as the time from initiation of study therapy to the date of the first documented tumor progression or death due to any cause. Participants who die without a reported prior progression will be considered to have progressed on the date of death. Participants who did not have disease progression or die will be censored at the date of last tumor assessment. Participants who did not have any on study tumor assessment and did not die will be censored at date of last follow-up. Participants who started any subsequent anti-cancer therapy without a prior reported progression will be censored at the last tumor assessment prior to initiation of the subsequent anti-cancer therapy, which excludes the surgical resection for differentiating radiology progression from pseudoprogression. Participants who had surgical resection for differentiating radiologic progression from pseudoprogression and tumor pathology confirms disease progression will be defined as progressive as of the date of radiographic progression that led to surgery. PFS will be determined by investigator reported response based on iRANO criteria (Section 6.4). Tumor assessment will occur every 8 weeks (+/- 1 week) until disease progression is documented. Subjects with non-measurable disease at baseline will be considered to have progressed if there is an appearance of new lesions consistent with tumor, any unequivocal increase in baseline enhancing disease, the unequivocal appearance of new tumor growth or re-growth at prior surgical sites, or clinical deterioration.

ORR is defined as the number of subjects whose best overall response (BOR) is confirmed CR or PR divided by response evaluable subjects (Section 11.1.2). The best overall response (BOR) is determined once all the data for the subject is known. BOR is defined as the best

CONFIDENTIAL

This document is confidential. Do not disclose or use except as authorized.

response designation, as determined by investigators, recorded between the date of study therapy initiation and the date of objectively documented progression per iRANO criteria (Section 11.5), the date of subsequent therapy, or date of surgical resection, whichever occurs first. For subjects without documented progression, subsequent therapy, or surgical resection, all available response designations will contribute to the BOR assessments. BOR will be determined by investigator reported response based on iRANO criteria.

Tumor assessments will occur every 8 weeks thereafter until disease progression is documented or the end of the study. For purposes of this protocol analysis, if a response evaluable subject discontinues from the study or receives a subsequent therapy prior to the 8-week tumor assessment, this subject will be counted in the denominator as a non-responder.

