Duration of Participation	
Each participant will participate in the trial from the time the participant signs the Informed Consent Form (ICF) through the final protocol-specified contact. After a screening phase (assessments within 14 days of first dose), eligible participants will receive treatment during each dosing cycle.
 
 
• Cohort 1: Nivolumab every 2 weeks
 
• Cohort 2: External Beam RT (IMRT, 3D-CRT, or proton-beam radiation therapy) followed by 4 cycles of Nivolumab + Ipilimumab (dosing every 3 weeks), followed by Nivolumab monotherapy (dosing every 4 weeks).
 
 
Treatment with study therapy will continue until: documented confirmed disease progression; unacceptable adverse event(s)*; intercurrent illness that prevents further administration of treatment; investigator's decision to withdraw the participant; participant withdraws consent; pregnancy of the participant; noncompliance with trial treatment or procedure requirements. After the end of treatment, each participant will be followed for 30 days for adverse event monitoring (serious adverse events will be collected until 100 days after the end of treatment or the start of new anti-cancer treatment, whichever comes first). Participants who discontinue for reasons other than disease progression will have post-treatment follow-up for disease status until disease progression, withdrawing consent, or becoming lost to follow-up. All participants will be followed by telephone or medical record review for overall survival until death, withdrawal of consent, or the end of the study.
 
* NOTE: Cohort 2 participants may proceed with nivolumab monotherapy dosing every 4 weeks if ipilimumab is considered toxic.

CONFIDENTIAL

This document is confidential. Do not disclose or use except as authorized.

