- a. All screening procedures to be performed within 14 days prior to start of study treatment, except informed consent (which may occur up to 28 days prior to start of study treatment).
- b. C1D1 and Day 1 of subsequent cycles:
  - For C1D1 only, screening assessments may serve as day 1 assessments, except pregnancy test (within 72 hrs of drug) and vital signs & oxygen saturation (within 3 days prior to drug), except in the event that there are any indications that the participant's condition is deteriorating for which laboratory evaluations should be repeated within 48 hrs prior to initiation
  - For all subsequent cycles, required assessments should be performed within 3 days prior to dose.
- c. *Intentionally blank*
- d. End of Tx: End of treatment assessments to be performed within 7 days after last day drug administration or within 7 days after decision to end treatment. Assessments may continue for ongoing reportable adverse events.
- e. 30-Day Post Drug: A contact/visit is to be performed at 30 days (+/-7 days) after date of last study drug administration. This may be performed via documented phone conversation with a study nurse or clinician or a clinic visit. All participants will be followed until resolution or stabilization of any serious or reportable adverse events occurring during treatment or starting within 30 days of last study drug.
- f. Active Follow-Up: Applies only to those pts who did not progress while on study therapy (including pts who start subsequent anti-cancer therapy), until documented disease progression or pt comes off study for some other reason. Participants will be followed every 3 months (+/- 1 month). See footnote x for scan schedule during Active Follow-Up. Once progression is confirmed, participants will enter long-term follow-up.
- g. Participants enter Long-Term Follow-Up after coming off active treatment for disease progression or after completion of Active Follow-Up: Participants will be followed every 3 months (+/- 1 month) via contact or medical record review until death for post-treatment therapies, reason for stopping those therapies, and survival.

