Progressive Disease	
Defined by any of the following:
 
 
• <math>\geq 25\%</math> increase in sum of the products of perpendicular diameters of enhancing lesions compared with the smallest tumor measurement obtained either at baseline (if no decrease) or best response, on stable or increasing doses of corticosteroids*;
 
• Significant increase in T2/FLAIR non-enhancing lesions on stable or increasing doses of corticosteroids compared with baseline scan or best response after initiation of therapy* not cause by co-morbid events (eg, radiation therapy, demyelination, ischemic injury, infection, seizures, postoperative changes, or other treatment effects);
 
• Any new lesion;
 
• Clear clinical deterioration not attributable to other causes apart from the tumor (eg, seizures, medication adverse effects, complications of therapy, cerebrovascular events, infection, and so on) or changes in corticosteroid dose; failure to return for evaluation as a result of death or deteriorating condition;
 
• Or clear progression of non-measurable disease.
 
 
Confirmation of radiographic progression should be performed on follow-up imaging for participants who are not developing significant neurologic decline felt to be attributable to underlying tumor growth as detailed in Section 11.4.

\* Stable doses of corticosteroids include subjects not on corticosteroids

Abbreviations: MRI, magnetic resonance imaging; FLAIR, fluid-attenuated inversion recovery

For purposes of this study, the minimum time from baseline for determination of SD will be 4 weeks.

CONFIDENTIAL

This document is confidential. Do not disclose or use except as authorized.

The iRANO Response Criteria to be used in this study are summarized in Table 11.2-2.

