#### 14.1.6.1 Efficacy Endpoints

Efficacy endpoints that will be evaluated for are listed below, followed by the descriptions of the derivations of selected endpoints.

The primary efficacy endpoint for this study is PFS-6, defined as the proportion of subjects in the analysis population who remain progression-free for at least six months following initiation of study therapy. Response for the primary analysis will be determined by the investigator assessment, and a confirmation assessment is required per iRANO.

Secondary efficacy endpoints include: (1) ORR defined as the proportion of subjects in the analysis population who have complete response (CR) or partial response (PR) using iRANO criteria as well as duration of response, defined as time from first iRANO response to disease progression in subjects who achieve a PR or better; (2) progression-free survival (PFS), defined as the time from allocation to the first documented disease progression according to iRANO or death due to any cause, whichever occurs first; and (3) overall survival (OS). Secondary endpoints will be assessed using standard descriptive statistics and the Kaplan Meier method to estimate median OS and PFS and rates at times of interest. Duration of response (DOR), defined as the time from first documented disease response to progression or death, whichever comes first.

Additional supportive analyses of best overall response rate, duration of response, and PFS will be conducted using iRANO criteria, in which a confirmation assessment of disease progression must be obtained at least 4 weeks after the initial disease assessment indicating progressive disease.

Nominal p -values may be computed for efficacy analyses as a measure of strength of association between the endpoint and the treatment effect rather than formal tests of hypotheses. Unless otherwise stated, all statistical tests will be conducted at the  $\alpha=0.05$  (2-sided) level.

CONFIDENTIAL

This document is confidential. Do not disclose or use except as authorized.

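### Secondary PFS censors a living participant with no on-study scan at an undefined last follow-up date, so unscanned time counts as progression-free; the bias is upward and probably small

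*Combined protocol and SAP*

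**What the plan says.** Section 14.1.2.2 measures PFS from initiation of study therapy and gives three censoring rules that matter here.

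- Scanned and event-free: "Participants who did not have disease progression or die will be censored at the date of last tumor assessment".
- Never scanned and alive: "Participants who did not have any on study tumor assessment and did not die will be censored at date of last follow-up".
- New anti-cancer therapy without prior reported progression: the participant "will be censored at the last tumor assessment prior to initiation of the subsequent anti-cancer therapy".

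Last follow-up is not defined. The Trial Summary states: "All participants will be followed by telephone or medical record review for overall survival". Footnote g of the study calendars has participants "followed every 3 months (+/- 1 month) via contact or medical record review until death for post-treatment therapies". Section 5.3 (Long Term Follow-Up) uses the same 3-month interval but adds future relapses to what is followed.

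Section 14.1.6.1 uses the "Kaplan Meier method to estimate median OS and PFS and rates at times of interest". It starts the PFS clock at allocation, whereas 14.1.2.2 starts it at initiation of study therapy. Under 14.2 the efficacy dataset is everyone who received at least one dose, so participants never scanned on study are included. Section 14 says that no separate SAP will be issued.

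**The concern.** The two neighbouring rules treat the same kind of information differently. A participant with a stable week-8 scan and no later one stops contributing at week 8. A participant with no on-study scan at all can stay in the risk set until a survival call many months later. The second participant has less evidence of being progression-free and is credited with more progression-free time.

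Keeping such participants at risk enlarges the Kaplan-Meier denominator with people in whom radiologic progression could not be seen. Each observed event then causes a smaller drop in the curve, so median PFS and the PFS rates come out too favourable. The natural comparison for a 6-month rate is the historical 26% in 14.1.4, so a few points matter for interpretation.

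The rules also collide. For a never-scanned participant who starts other therapy, one rule gives last follow-up, possibly after that therapy began. The other gives a last tumor assessment that, on study, does not exist.

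ORR is handled in the opposite spirit: 14.1.2.2 counts a response-evaluable subject who leaves before the 8-week assessment as a non-responder.

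**Working it through.** **The plan's own figures.** The plan gives no figure for this censoring rule. Its stated figures belong to PFS-6, and they reproduce by exact binomial calculation without any censoring date:

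- P(X ≥ 10 | n = 25, p = 0.26) = 0.0893 (stated 0.089).
- P(X ≥ 10 | n = 25, p = 0.51) = 0.904 (stated 90%).
- P(X ≤ 2 | n = 10) = 0.496 at p = 0.26 and 0.048 at p = 0.51 (stated 0.5 and 0.048).

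**Inputs for the secondary PFS check.** From 14.1.4: 25 participants per cohort and a 6-month rate of 26%. Assumed, because the documents do not give them: exponential PFS, events observed continuously, k = 1, 2 or 3 living participants never scanned on study, and their last follow-up at c months.

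**Formulas.** The rate is λ = −ln(0.26)/6 = 0.2245 per month, so the true median is ln(2)/0.2245 = 3.1 months. If the k participants stay in the risk set without an event until c, the expected 6-month estimate is approximately:

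- c < 6: S(6) = [k/25 + (1 − k/25)·exp(−0.2245c)] · exp(−0.2245(6 − c))
- c > 6: S(6) = [k + (25 − k)·0.26]/25

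Example with k = 1 and c = 3: exp(−0.2245·3) = 0.5099, so S(6) = (0.04 + 0.96·0.5099)·0.5099 = 0.270.

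| Last follow-up | 6-month rate, k = 1 / 2 / 3 | Median in months, k = 1 / 2 / 3 |
|---|---|---|
| 2 months | 26.6% / 27.2% / 27.8% | 3.2 / 3.3 / 3.4 |
| 3 months | 27.0% / 28.0% / 29.0% | 3.3 / 3.4 / 3.6 |
| 4 months | 27.5% / 29.0% / 30.5% | 3.3 / 3.5 / 3.7 |
| beyond 6 months | 29.0% / 31.9% / 34.9% | 3.3 / 3.5 / 3.7 |

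**Cross-check.** A Kaplan-Meier simulation (2,000 trials of 25) gave mean 6-month estimates of 0.269, 0.279 and 0.289 with last follow-up at 3 months, and 0.289, 0.318 and 0.348 at 6 months or later. Censoring the same participants at start of therapy gave 0.259 for each k, equal to the simulated value with nobody affected.

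**If missing scans are informative.** Suppose the k participants had in fact all progressed by month 6. The true rate is then (25 − k)·0.26/25 = 25.0%, 23.9% or 22.9%, and censoring at start of therapy would still report about 26%.

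**The case against.** The strongest reply is that few participants can be affected and that their follow-up is not blind. To be caught by the rule, a treated, living participant must miss the week-8 scan, the end-of-treatment MRI scheduled in both study calendars, and all imaging in active follow-up. Table 11.2-1 already counts as progression "failure to return for evaluation as a result of death or deteriorating condition", and clear clinical deterioration attributable to the tumor is progression without a scan. Section 5.3 includes future relapses in long-term follow-up, although the Trial Summary and footnote g do not mention them. Those left over are mostly early withdrawals or losses, whose last follow-up is early.

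Most of this stands. It rules out reading all unscanned time as unobserved, and it makes the bottom row of the table remote: nothing in the documents suggests that three of 25 participants would be never scanned yet followed past six months. It does not remove the inconsistency between the rules or the collision at new therapy.

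A further fair objection is that censoring at start of therapy is unbiased only if missing scans are non-informative. That is correct. It is a reason to add a sensitivity analysis, not to keep the present date.

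A reader might also infer that the primary result is biased. The documents do not support that. PFS-6 is a "proportion of participants in the analysis population who remain progression-free for at least six months following initiation of study therapy", decided by a count of at least 10, and the censoring sentence sits in the definition of the secondary endpoint. Section 14.1.2.1 does not say how a never-scanned participant is counted, but this sentence does not supply the answer.

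**Conclusion.** The concern holds as a minor defect in a secondary, descriptive endpoint. As written, the rule biases Kaplan-Meier PFS upward whenever a living participant has no on-study scan, and it gives no usable date for such a participant who starts new therapy.

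With last follow-up at 2 to 3 months, the more plausible case, the bias is 0.6 to 3.0 percentage points on a true 6-month rate of 26% (26.6% − 26% to 29.0% − 26%). The median rises by about 0.1 to 0.5 months. The upper bound of 8.9 points (34.9% − 26%) should not be quoted as an expected effect. All of these sizes rest on assumed counts, assumed follow-up times, exponential PFS, and the same underlying risk in scanned and unscanned participants. To the extent that clinical progression is picked up in unscanned participants, the bias is smaller.

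**What to change.** 1. In 14.1.2.2, censor participants with no on-study tumor assessment, no documented progression (radiologic or clinical) and no death at the date of initiation of study therapy. State that this also covers those who start subsequent anti-cancer therapy.
2. In 14.1.6.1, use the same PFS time origin as 14.1.2.2, in place of allocation.
3. Add a sensitivity analysis that counts these participants as events at an early date fixed in advance. Under the assumptions above, its expected 6-month rate is 25.0%, 23.9% or 22.9% for k = 1, 2 or 3.
4. Reconcile the passages on tumor assessment after treatment stops and after new therapy. Section 5.3 (Treatment Phase) runs assessments to the later of progression or discontinuation. Section 5.3 (Active Follow-Up) leaves the intervals to the investigator and ends at new therapy. Calendar footnotes f and x also leave scan timing to the investigator but continue after new therapy. Section 14.1.2.2 says every 8 weeks until progression is documented, and in its ORR text until progression or the end of the study.

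The cost of the censoring change is about one sentence, but with no separate SAP it has to be a protocol amendment with IRB approval (13.1 and 14). Secondary PFS will look slightly less favourable, and participants censored at time zero add no information to the curve. Primary alpha, power and the interim rule do not change. Item 4 may change the number of scans, depending on which text is kept.
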